The 22-gauge core biopsy needle with reverse bevel design (EchoTip® Procore™) will be compared prospectively to the standard straight hollow-core 22-gauge or 25-gauge FNA needle already used in our clinical practice for the diagnosis of solid pancreatic lesions. The needles to be used in this study are FDA-approved, commercially available and currently in use at MDACC.

EUS FNA 22/25-gauge Needle	EUS FNA 22-gauge Needle
Straight Hollow-Core Needle	Reverse Bevel Design
Collect only Cells	Collect Cells and Tissue

Interventions:

Patients who are referred for EUS guided FNA and who consent to participate will have their examination performed using two different needles. As part of the study two passes will be performed with the standard 22-gauge or 25-gauge straight hollow core needle and two passes will be

performed using the 22-gauge EchoTip® Procore™ needle. All passes will be taken from a single lesion and from the same endoscopic location. All passes will be numbered. Both passes taken with the standard needle will be sent for immediate cytologic evaluation as is standard. One of the 22-gauge EchoTip® Procore™ passes will be sent for immediate cytologic evaluation and one pass will be sent for histology. Additional non-study passes will be obtained if necessary (after immediate cytologic evaluation of the three initial passes) using needle of endoscopist's choice. If adequate sampling is believed to have been obtained in fewer than 4 total passes as confirmed by immediate cytologic assessment then no additional passes need be performed at the discretion of the endoscopist and analysis will be performed with existing data. All other elements of the exam will be otherwise unchanged. The endoscopist performing the procedure will alternate the sequence of EUS needles used in any given patient. In addition we will alternate which Procore™ pass is sent for histology and cytology. The primary intervention will be which needle is used and in which sequence. The reason for alternating sequence is to eliminate any confounding variable associated with sequence such as increased bloody aspirate or possible variability in cytologic yield related to increased number of passes. The study does not involve an increased or excessive number of passes or other additional interventions beyond what would be current standard practice. This procedure will be explained to subjects at time of consent.

Cytopathologic Evaluation:

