The specimens are to be assessed independently by members of the MDACC cytology/pathology department who will be blinded to the needle sequence and type of needle used. For the purposes of the study cytopathologic results will be recorded from the slides of each of the numbered individual passes taken. Reports for immediate assessment purposes will be based on the 3 passes sent to cytology and any additional passes required outside the study including the cellblock made from wash of all needle passes. The cytological specimen quality will be graded on cellularity and other features

comparable to the assessment in our earlier study by Lee et al. (10) (see Appendix E & F). The single Procore™ sample sent to histology will be processed like any other endoscopic biopsy specimen (immediate assessment not possible as with cytology due to processing requirements) and the final pathology report will be used for comparison purposes to the cytological specimen results.

Study Duration:

The expected duration of the study is approximately 2 years from the commencement of subject enrollment. Subject enrollment is expected to be up to one year. All subjects will be followed until surgery, death, or at least six months until last subject enrolled.

6. Biostatistical Analysis

Study design

The primary objective of the study is to assess if the 22-gauge EchoTip® Procore™ needle has a better diagnostic performance compared to standard 22-gauge and 25-gauge straight hollow core needles (both 22-gauge and 25-gauge needles are used interchangeably). The primary endpoint is whether or not the needle pass result provides diagnostic material (yes vs. no). For each patient, both needles will be used to sample the same lesion. Two needle passes will be performed with each needle type. The average number of needle passes needed to obtain a diagnostic specimen of solid lesions in the pancreas is four using the standard 22-gauge or 25-gauge straight hollow core needle in our practice (although the number of passes can be variable in any given lesion for a variety of reasons). All needle passes will be numbered and evaluated individually. For the two passes taken from the straight hollow-core standard-needle, the specimens are to be assessed by cytology for immediate review. For the two passes taken with the EchoTip® Procore™ needle, one pass will be submitted to cytology for immediate review and one pass for pathology (immediate review not

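### Could the pass numbers reveal the Procore slide to the cytologist and undo the blinding?

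*Combined protocol and SAP*

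**What the plan says.** Blinding is stated three times. Section 5 (Cytopathologic Evaluation) and section 9 (Independent Monitoring of Source Data) have specimens assessed independently by staff "who will be blinded to the needle sequence and type of needle used". Section 6 (Primary Endpoint) makes the same blinding part of the endpoint, which is the yes/no Diagnostic item in Appendix E.

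On identification, section 5 (Interventions) says "All passes will be numbered", and Cytopathologic Evaluation adds that "cytopathologic results will be recorded from the slides of each of the numbered individual passes taken". Neither gives a rule for assigning numbers or says what the reader sees on a slide.

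On the flow of specimens, each patient has two standard and two Procore passes. Both standard passes go to cytology. Of the Procore pair, one of the "passes will be sent for immediate cytologic evaluation and one pass will be sent for histology". The order varies in two ways: "The endoscopist performing the procedure will alternate the sequence of EUS needles used in any given patient", and "In addition we will alternate which Procore™ pass is sent for histology and cytology". The permitted orders are not listed. Sampling may also end early: "If adequate sampling is believed to have been obtained in fewer than 4 total passes as confirmed by immediate cytologic assessment", the endoscopist may stop.

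Section 5 mentions a second use of the same slides: "Reports for immediate assessment purposes will be based on the 3 passes sent to cytology", together with any extra passes and the cell block.

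**The concern.** The pass number is the only specimen identifier that the text describes. The study code in section 7 links data to a subject for confidentiality and does not mask slides. With four passes, cytology receives two standard slides and one Procore slide, and the absent number belongs to the other Procore pass. A reader who sees sequential numbers and knows how the needles alternate could work back from the gap to the Procore slide.

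The primary endpoint is a judgement made on each pass, and the sample size assumes that Procore does better (85% against 65%). A reader who knew the needle could lean one way without meaning to. Masking is the main protection against that in a within-patient comparison, and the plan promises it without saying how it is kept. Random slide codes, with the key held by someone other than the readers, look like an easy safeguard.

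**Working it through.** **Plan figure.** The documents give no figure on labelling. Their one design calculation is 60 patients for about 80% power by McNemar's test, with a difference of 0.20 and a discordant proportion of 0.30. The discordant cells are then 0.25 and 0.05 (0.25 − 0.05 = 0.20; 0.25 + 0.05 = 0.30). The exact conditional test at n = 60 has power 79.7%, which agrees with the plan. Slide labelling does not enter this calculation.

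**How much the numbers could reveal.** Let S be a standard pass and P a Procore pass. Inputs from section 5: two S, two P, and one P diverted to histology. Assumptions not in the documents: the orders in use are equally likely, either P is equally likely to be diverted, all four passes are taken, and one reader sees all of the patient's cytology slides and knows the scheme.

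There are M = 2 × (number of orders) combinations of order and diverted pass. For each set of numbers the reader could see, count the combinations that place the Procore slide at each number and keep the largest count. The probability that the best guess is right is the sum of those largest counts divided by M.

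Example, SSPP/PPSS with passes numbered 1–4:
- 3 missing: Procore is slide 4
- 4 missing: Procore is slide 3
- 1 missing: Procore is slide 2
- 2 missing: Procore is slide 1

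Each set of numbers has one answer, so the result is 4/4.

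If only the cytology slides are numbered, 1–3, there is no gap. The Procore slide then falls at 3, 3, 1, 1 for SSPP/PPSS, at 3, 2, 2, 1 for SPSP/PSPS, and at 2, 2, 3, 1 for SPPS/PSSP. The best guess is 2/4 in each case.

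| Orders in use | M | Passes numbered 1–4 | Cytology slides numbered 1–3 |
|---|---|---|---|
| SSPP, PPSS | 4 | 4/4 = 100% | 2/4 = 50% |
| SPSP, PSPS | 4 | 4/4 = 100% | 2/4 = 50% |
| SPPS, PSSP | 4 | 4/4 = 100% | 2/4 = 50% |
| SSPP, PPSS, SPSP, PSPS | 8 | 4/8 = 50% | 3/8 = 37.5% |
| All six | 12 | 4/12 = 33% | 4/12 = 33% |

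Chance with three slides is 1/3 = 33%, which is also what a random label would leave.

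**Early stopping, passes numbered in sampling order.** If study passes stop after three, a Procore slide reaches cytology in 3/4 of combinations under each mirrored pair, and it can still be named in all three of those. If they stop after two, it reaches cytology in 2/4. Under SPSP/PSPS and SPPS/PSSP the guess is then 1/2, which is chance with two slides. Under SSPP/PPSS only one needle has been used. The documents do not say how often stopping occurs.

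**What the text supports.** The 100% figure needs all of the following:
- numbers that follow sampling order: not stated
- numbers visible to the reader: not stated, and at odds with the stated blinding if they reveal the needle
- a reader who knows the alternation scheme: not stated
- one reader seeing all of a patient's cytology slides: not stated; section 5 speaks of independent assessment by members of a department, and section 6 of rating each pass individually
- a two-order scheme: not stated
- enough passes taken: usual, but not guaranteed

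**The case for a change.** The strongest case for acting is that a promise of blinding cannot be audited, while a slide code and a key-holder can. The endpoint is subjective, the needle order is alternated rather than randomised, and the word alternate does not suggest six equally likely orders. The near-certain rows of the table are therefore not far-fetched if numbers are sequential and visible. Section 5 can also be read as separating the study results from the immediate report, so a later coded read of at most 3 × 60 = 180 cytology passes would fit without extra passes or patients.

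The arithmetic stands, and so does the observation that no mechanism is written down. The step from there to a needed change does not.
- The stated blinding binds whoever labels the slides. Showing numbers that reveal the needle would depart from the plan.
- Appendices A to D are not in the text available, so a labelling form may already exist.
- The separation of the two reads is only one reading. Section 5 lists specimen adequacy under immediate outcomes, and sections 5 and 6 send the cytology passes for review during the procedure. If that on-site read is the study rating, codes cannot hide the order in which slides arrive.
- If a separate read were added, it could need extra reader time, for which the documents give no figure.
- Codes also cannot hide any visible difference in Procore material, which section 5 (Devices) describes as cells and tissue. Nor can they mask needle type on the histology specimen, which is always Procore.

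**Conclusion.** No change is called for. The plan commits to blinding by needle type and sequence in three places and leaves slide labelling to the laboratory. That is a gap in operational detail which staff following the protocol would be expected to fill sensibly.

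The possible leak runs from chance (33%) to 100% with four passes numbered in sampling order, and from 33% to 50% if only cytology slides are numbered. Every figure above chance depends on visible order-based numbers and a reader who knows the scheme and sees the patient's slides together. The documents establish none of these. They do not show that blinding fails, no direction or size of rating bias can be derived from them, and the sample size and power are unaffected. Recoding slides would bring an uncertain gain, because it may not reach the read that counts. A sentence saying which read is the study rating and how slides are labelled would be a courtesy to the reader; the analysis does not depend on it.

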Appendix F.

Histology Rating

Criteria	Scale	Rating
Diagnostic	Yes	
	No

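### The histology result compared with cytology comes from the routine pathology report, with no step withholding the earlier cytology result, and the stated needle blinding cannot hold for histology (minor).

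*Combined protocol and SAP*

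**What the plan says.** Section 5, Interventions, allocates the four study passes. For the standard needle: "Both passes taken with the standard needle will be sent for immediate cytologic evaluation as is standard". For the new needle: "One of the 22-gauge EchoTip® Procore™ passes will be sent for immediate cytologic evaluation and one pass will be sent for histology".

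Section 5, Cytopathologic Evaluation, calls for independent assessment: "The specimens are to be assessed independently by members of the MDACC cytology/pathology department". The only masking it specifies is that these are readers "who will be blinded to the needle sequence and type of needle used". Section 9, Independent Monitoring of Source Data, repeats this. Neither place defines independence or mentions masking one specimen's reader to another specimen's result.

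The same part of Section 5 describes the histology specimen: "The single Procore™ sample sent to histology will be processed like any other endoscopic biopsy specimen". It adds that immediate assessment is not possible for this pass, and that "the final pathology report will be used for comparison purposes to the cytological specimen results".

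Section 5, Immediate outcomes, and Section 6, Study design, provide a separate study rating: each pass is reviewed and rated on its own, using Appendix E for cytology and Appendix F for histology. Appendix F, headed "Histology Rating", has one item, diagnostic yes or no, with no criteria and no place for the diagnosis.

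Section 6 names two secondary endpoints: whether the Procore specimen is adequate for histologic diagnosis, and how cytological diagnosis from both needles compares with the Procore histology. The primary endpoint is a cytology read by readers blind to needle and sequence.

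**The concern.** Two things looked wrong.

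First, the masking statement covers all specimens, but every study specimen that reaches histology was taken with the Procore needle. A pathologist who knows the design knows the needle.

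Second, masking to needle is not the protection that the cytology-histology comparison needs. That comparison is informative only if each result is reached without the other. Here one result is produced during the procedure, and the other is taken from a later clinical report whose author is not kept from the first. A scanty core, judged on a yes/no item without criteria, is the kind of specimen on which prior knowledge can sway the reading.

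At stake is how far the reported agreement between cytology and the core can be trusted, and to a lesser degree the histologic adequacy rate. The needle's claimed advantage is that it yields tissue, so these secondary results bear on the study's purpose.

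**Working it through.** **The plan's own figure.** Section 6 gives 60 patients for about 80% power with McNemar's test, a difference of 0.20, a discordant proportion of 0.30 and two-sided 5% significance. The discordant cells are (0.30 + 0.20)/2 = 0.25 and (0.30 − 0.20)/2 = 0.05. Full enumeration of the exact two-sided test at N = 60 gives 79.7%, so the figure reproduces. This point does not change it.

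**Step 1: can needle blinding hold for histology?**

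| Needle | Passes to cytology | Passes to histology |
|---|---|---|
| Standard | 2 | 0 |
| Procore | 1 | 1 |

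All histology passes are Procore, so it cannot hold for a reader who knows the design. With no standard-needle histology, knowing the needle cannot distort a between-needle histology comparison.

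**Step 2: which result exists first?** The three cytology passes are assessed during the procedure and determine whether more passes are needed. Histology cannot be assessed then. The on-site cytology result therefore precedes the pathology report. The documents do not date the study ratings of the numbered cytology slides, so the order is certain only for the on-site result.

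**Step 3: which histology value feeds which endpoint?** Section 5 names the final pathology report only for the comparison with cytology. Adequacy is based on review of each pass with Appendix F. Nothing masks either source to cytology.

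**Step 4: how far could agreement move?** The documents give neither the true agreement A nor the share f of would-be disagreements in which the histology result follows the known cytology. Both are assumptions here.

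Observed agreement = 1 − (1 − A)(1 − f)

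| A | f = 10% | f = 25% | f = 50% |
|---|---|---|---|
| 60% | 64% | 70% | 80% |
| 70% | 73% | 77.5% | 85% |
| 80% | 82% | 85% | 90% |

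For example, with A = 70% and f = 25%: 1 − 0.30 × 0.75 = 0.775. With 60 patients and A = 80%, there are 0.20 × 60 = 12 true disagreements, of which f = 25% hides 3 and f = 50% hides 6. Sixty is the largest possible denominator, because Section 5 lets the endoscopist stop before four passes.

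**Step 5: which way would adequacy move?** Following cytology changes the histology diagnostic rate by f × (share with diagnostic cytology only − share with diagnostic histology only). The power assumptions are borrowed purely to illustrate, with cells of 0.60 both diagnostic, 0.25 and 0.05 discordant, and 0.10 neither.

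- If histology is the 85% margin and cytology the 65% margin, the change is f × (0.05 − 0.25). The rate falls from 85% to 83%, 80% and 75% at f = 10%, 25% and 50%. Agreement rises from 70% to 73%, 77.5% and 85%, and kappa from 0.24 to 0.33, 0.45 and 0.65.
- If the margins are reversed, the change is f × (0.25 − 0.05). The rate rises from 65% to 67%, 70% and 75%.

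Agreement goes up in both cases. Adequacy goes down in one and up in the other.

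**Step 6: does it reach the primary comparison?** Section 6, Statistical Analysis, compares the standard passes with one Procore pass, and the primary endpoint is a cytologist's determination. On that reading the histology result stays out. Section 6, Power and Sample Size, instead assumes that two Procore passes are diagnostic in 85% of patients, and one of those two is the histology pass. On that reading it enters.

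**The case against.** The strongest reply is that the protocol already calls for independent assessment and for each pass to be rated individually, and never says that the pathologist sees the cytology result. That stands as far as it goes: independence is stated. But the term is not defined, the only masking spelled out concerns needle and sequence, and the same part of Section 5 takes the compared value from a routine report. Independence is stated without being put into operation.

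A reader might infer more than the documents support:

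- *That bias has been shown.* It has not. The documents leave the route open; they do not say it is used.
- *That the bias favours Procore.* Step 5 shows that adequacy could fall as well as rise. Higher agreement does not clearly favour Procore either: histology is compared with cytology from both needles, so closer agreement would credit the standard needle too and suggest that the core adds less.
- *That adequacy is taken from the clinical report.* The protocol bases adequacy on review of each pass with Appendix F. The remaining gap is that this rating is not masked to cytology.
- *That loss of needle blinding is itself damaging.* With no standard-needle histology, it calls mainly for a wording correction.

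Two further objections stand. The protocol specifies no formal test for this secondary comparison, which limits the consequence. And replacing the report with Appendix F in its present form would reduce a comparison of diagnoses to yes/no concordance, so the form needs a diagnosis field.

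**Conclusion.** The point holds as a minor one. The needle-blinding statement is wrong for histology on the protocol's own allocation of passes, with little consequence. The cytology-histology comparison uses a report issued after on-site cytology, with no step withholding that result, so agreement is open to inflation. The size cannot be determined from the documents; the range in Step 4 rests wholly on assumed values of A and f. The direction of any effect on histologic adequacy is undetermined, so a claim that the plan tilts the results towards Procore is not supported.

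The consequence is confined to secondary endpoints if the primary test uses one Procore cytology pass, as Statistical Analysis and Primary Endpoint in Section 6 indicate. If the two-pass Procore result in Power and Sample Size is analysed instead, a histology read that is masked neither to needle nor to cytology enters the primary comparison.

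**What to change.** 1. In Section 5 (Cytopathologic Evaluation) and Section 9, limit the needle-blinding statement to the cytology passes, and say that histology is not blinded to needle.
2. Add a diagnosis field to Appendix F.
3. Require the histology reader to record diagnostic yes/no and the diagnosis from the slide before opening the cytology result.
4. Use that record, not the final pathology report, for the cytology-histology comparison and for histologic adequacy. The clinical report is issued as usual.
5. Reconcile Power and Sample Size with Statistical Analysis in Section 6 on whether the primary comparison uses one Procore pass or two.

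The cost is protocol wording, one added field, and completing one form before sign-out. No extra specimen or slide is needed, and items 1 to 4 leave the sample size unchanged.

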possible). Any additional passes will not be included in the study. The need for additional passes will be determined based on the three passes (two straight hollow-core standard FNA needle and one EchoTip® Procore™ needle) sent for immediate cytologic assessment during the procedure as is routine at our center. Immediate assessment is not possible for the one pass submitted for histologic analysis with the EchoTip® Procore™. Each needle pass submitted for review will be rated individually by the cytologist/pathologist (see appendix E & F for cytopathology rating sheet as applicable). A final analysis will be performed on the diagnostic results from each needle pass. For the purpose of the study, if the passes are adequate to be diagnostic, the result will be considered “yes”. If the passes are inadequate, the result will be considered “no”. Equal number of biopsies will be taken for each needle sequence.

Power and Sample Size:

The two standard straight hollow-core FNA passes are assumed to be diagnostic in 65% of patients. The two Procore™ needle passes are assumed to be diagnostic in 85% of patients. Assuming a discordant proportion of 30%, a sample size of 60 patients will be needed to achieve 80% at a 5% significance level.

For the comparison, McNemar's test will be used for the sample size justification. Our null and alternative hypotheses are:

$$H_0: P_a - P_b = 0 \text{ vs. } H_a: P_a - P_b \neq 0$$

Where P_a and P_b are the diagnostic proportions for the 22-gauge EchoTip® Procore™ needle and standard 22-gauge or 25-gauge straight hollow core needle respectively.

Table 1 displays in the scenario the sample sizes needed to achieve about 80% power with a two-sided significance level of 0.05 for different scenarios with different assumptions for proportion discordant.

Sample size	Difference in positive proportions	Proportion Discordant	power
60	0.2	0.3	0.8

In this study, we assume that the 22-gauge EchoTip® Procore™ needle will have a higher diagnostic yield (85%) than a standard straight hollow-core FNA needle after two passes (65%). A sample size of 60 patients will achieve about 80% power at a 5% significance level using a two-sided inequivalence test of correlated proportions when it is assumed that there is 20% difference regarding biopsy result (positive vs. negative) and the discordant proportion is 30%.

Statistical Analysis:

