Data analysis will be performed using SAS as appropriate. Intent-to-treat data will be used for primary analysis. Demographic and disease characteristics of the patients at registration will be summarized using descriptive statistics such as mean, standard deviation (SD), median and range. Biopsy result (diagnostic proportion) from each needle type will be presented with 95% confidence intervals. McNemar test will be used to compare diagnostic ability (yes vs. no) between the two pass information obtained from the standard straight hollow-core needle (22-gauge or 25-gauge) and the one pass information obtained from the 22-gauge EchoTip® Procore™ needle. In addition, McNemar test will be used to compare diagnostic ability (yes vs. no) between either of the two pass information obtained from the standard straight hollow-core needle (22-gauge or 25-gauge) and the one pass information obtained from the 22-gauge EchoTip® Procore™ needle.

Demographics and Other Characteristics:

Summary statistics for patients' demographics and other characteristics will be presented descriptively.

Primary Endpoint:

Comparison of a diagnostic cytopathology specimen provided from FNA of a solid pancreatic lesion using the two different needles as determined by a cytologists who will be blinded to needle type and sequence.

Secondary Endpoint:

Assessment of adequate specimen for histologic diagnosis with Procore™ needle of a solid pancreatic lesion. Comparison of cytological diagnosis from both needle types with histological assessment of Procore™ needle specimen.

7. Risks and Discomforts

There is not expected to be any increased risk with use of either needle above and beyond what is standard for the procedure. Both needles used in the study are already FDA approved, commercially available and used in clinical practice, including here at MD Anderson. Both needles are similar in size. There is no increased number of passes performed as part of this study. In addition it would not be possible to determine any specific procedure related complication to use of one needle verses the other in the setting of this study. We will keep track of the overall frequency of adverse events that are standard to the procedure.

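### The 80% power at 60 patients is for two Procore passes, but both planned McNemar tests use one

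*Combined protocol and SAP*

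**What the plan says.** **Sizing (Section 6, Power and Sample Size).** Two assumptions are stated side by side: "The two standard straight hollow-core FNA passes are assumed to be diagnostic in 65% of patients" and "The two Procore™ needle passes are assumed to be diagnostic in 85% of patients". With 30% discordance and a two-sided 5% McNemar test, 60 patients are said to give 80% power. The closing sentence of the same subsection repeats 85% and 65%, but attaches the count of two passes only to the standard needle.

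**Analysis (Section 6, Statistical Analysis).** Two McNemar tests are planned. The first sets the two-pass standard result against "the one pass information obtained from the 22-gauge EchoTip® Procore™ needle". The second keeps the same Procore side and changes the standard side to "either of the two pass information obtained from the standard straight hollow-core needle". Neither is labelled primary.

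**Where the passes go (Section 5, Interventions).** "One of the 22-gauge EchoTip® Procore™ passes will be sent for immediate cytologic evaluation and one pass will be sent for histology".

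**Endpoint (Section 6, Primary Endpoint).** "Comparison of a diagnostic cytopathology specimen provided from FNA of a solid pancreatic lesion using the two different needles". Adequacy for histology is a secondary endpoint.

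**The concern.** The sample size is argued for two Procore passes against two standard passes. Each planned test has a single Procore pass on one side. This does not look like a slip in the analysis text: both tests say one pass, and the design supplies only one Procore cytology pass per patient. A two-pass Procore result would combine one cytology and one histology pass, which does not match the cytological primary endpoint.

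The sizing paragraph is the only justification for 60 patients. If it describes a comparison that will not be made, readers of a non-significant result cannot tell whether the trial had the power it claims. Combining both Procore passes later, to match the sizing, would change the test.

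**Working it through.** **Inputs from Section 6, Power and Sample Size:** two-pass standard yield 0.65, two-pass Procore yield 0.85, difference δ = 0.20, discordance D = 0.30, n = 60, two-sided α = 0.05. The documents give no one-pass yield for either needle, no rule for combining two passes into one yes/no result, and no McNemar version (exact or asymptotic).

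**Step 1: the plan's own figure.** The normal approximation gives

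n = [1.96·√D + 0.8416·√(D − δ²)]² / δ² = [1.96·√0.30 + 0.8416·√0.26]² / 0.04 = 56.4, so 57.

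For the exact test, the number of discordant pairs is M ~ Binomial(60, D). Given M, the pairs favouring Procore are Binomial(M, (D + δ)/(2D)), here 0.50/0.60 = 0.833. The test rejects when the two-sided exact binomial p-value is at most 0.05. Summing over M gives 79.7% at n = 60, and the smallest n for 80% is 61. By enumeration at n = 60, the uncorrected chi-square version gives 85.7% and the continuity-corrected version 77.9%. The stated 80% is right for its own inputs.

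**Step 2: the first planned test.** The standard side stays at 0.65 (two passes) and the Procore side becomes an assumed one-pass yield p, so δ = p − 0.65. Power at n = 60:

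| Assumed p | δ | Exact, D = 0.20 | Exact, D = 0.30 | Exact, D = 0.40 | Uncorrected, D = 0.30 |
|---|---|---|---|---|---|
| 85% | 0.20 | 98.8% | 79.7% | 63.5% | 85.7% |
| 80% | 0.15 | 70.5% | 49.5% | 37.2% | 58.9% |
| 77.5% | 0.125 | 49.6% | 34.5% | 25.9% | 43.6% |
| 75% | 0.10 | 30.8% | 22.1% | 16.9% | 29.7% |
| 70% | 0.05 | 8.2% | 7.1% | 6.1% | 10.9% |

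At D = 0.30, the n needed for 80% exact power is 61 at p = 85%, 112 at 80%, 159 at 77.5% and 249 at 75%.

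**Step 3: when about 80% survives.** With the exact test it holds at p = 85% and D = 0.30, at p = 82.5% with D up to about 0.23, and at p = 80% with D up to about 0.17 (81.5% at 0.17, 77.5% at 0.18). D cannot be smaller than δ, so at p = 77.5% the minimum is D = 0.125, where exact power is 77.7%. That ceiling belongs to the exact test: the uncorrected version gives 95.2% there and 83.9% at D = 0.14.

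**Step 4: what 85% for two passes implies for one.** This depends on the undefined combining rule.
- If it means at least one pass is diagnostic and the second pass never adds a diagnosis, p = 85%.
- If it means at least one, with independent passes of equal yield, p = 1 − √0.15 = 61.3%, below the 65% comparator.
- If it means both passes are diagnostic, p is at least 85%.

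**Step 5: the second planned test.** Its wording is ambiguous. Read as one pass against one pass, with at-least-one yields and independent passes of equal yield, the standard side is 1 − √0.35 = 40.8% and δ = 0.613 − 0.408 = 0.204 before rounding. Exact power at n = 60 is then 91% at D = 0.25, 82% at D = 0.30 and 53% at D = 0.52, the last being the discordance if the two needles' results were also independent (0.613·0.592 + 0.408·0.387 = 0.52). This test may or may not reach 80%; no input in the documents decides it.

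**The case against.** The closing sentence of the sizing subsection can be read as 85% for the Procore needle with no pass count. On that reading the sizing fits the first planned test and 79.7% applies. The hypotheses are also stated by needle, and the Study design text defines the endpoint by needle pass without limiting it to cytology, so a needle-level result that includes the histology pass is conceivable. If two passes being diagnostic means both are, the one-pass yield is at least 85% and power at D = 0.30 is no lower than stated. The 61.3% case is an extreme: all passes come from one lesion and one endoscopic location, so positive correlation is likely, and equal yield for a cytology and a histology pass is not established. Type I error, estimates and confidence intervals are unaffected. Table 1 may have lost rows in the reading of the PDF.

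Much of this stands as a limit on size: a power loss is not demonstrated, and 61.3% should not be taken as an expected value. It does not remove the mismatch. The favourable reading of the closing sentence contradicts the explicit two-pass statement in the same subsection. The needle-level reading conflicts with the stated primary endpoint and with both tests as written. The both-passes reading is nowhere stated.

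**Conclusion.** The concern holds. The stated 80% is correct for two Procore passes against two standard passes, and no planned test makes that comparison. For the first test it carries over if one Procore pass is diagnostic in 85% of patients with discordance still at 0.30, or under other combinations of yield and discordance that the plan does not state.

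The effect on power is a range. With two standard passes at 65%, n = 60, D = 0.30 and the exact test, it runs from 79.7% at an assumed one-pass yield of 85% to 7.1% at 70%; a five-point fall from 85% to 80% takes it to 49.5%. Lower discordance, the uncorrected test or a one-pass yield above 85% would raise it; higher discordance would lower it. The second test is not sized at all. Because this is the sole basis for the sample size, it must be corrected, whether the true loss is small or large.

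**What to change.** Reconcile the two subsections of Section 6 in one of two ways.

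(a) Keep the tests and restate the sizing for them. Possible wording: *Two standard passes are assumed diagnostic in 65% of patients and one Procore cytology pass in [yield, with source]. With discordance [x], 60 patients give [y]% power (two-sided McNemar, [exact or asymptotic], 5% level).*

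(b) Keep the sizing and align the primary test with it. The plan must then define how one cytology and one histology pass form a single Procore result, and reconcile that with the cytological primary endpoint.

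In either case:
- Label which McNemar test is primary, and say what the second test compares.
- State the number of Procore passes in the closing sentence of Power and Sample Size, and the rule for combining passes.
- Table 1 is announced as covering "different scenarios with different assumptions for proportion discordant", but in the text available it has one row. Under (a), show power there for one-pass yields from 70% to 85% and discordances of 0.20, 0.30 and 0.40.

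The cost is one rewritten paragraph, the table and a few words in the analysis text. The sample size of 60 can stay. The downside is that the stated power may become less favourable.
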